5.3.2. Reporting Serious Adverse Events

An adverse event or suspected adverse reaction is considered "serious" if, in the view of the investigator, it results in any of the following outcomes:

- Death
- A life-threatening adverse drug experience any adverse experience that places the patient, in the view of the initial reporter, at immediate risk of death from the adverse experience as it occurred. It does not include an adverse experience that, had it occurred in a more severe form, might have caused death.
- Inpatient hospitalization or prolongation of existing hospitalization
- A persistent or significant incapacity or substantial disruption of the ability to conduct normal life functions.
- A congenital anomaly/birth defect.

Important medical events that may not result in death, be life-threatening, or require hospitalization may be considered a serious adverse drug experience when, based upon appropriate medical judgment, they may jeopardize the patient or subject and may require medical or surgical intervention to prevent one of the outcomes listed in this definition. Examples of such medical events include allergic bronchospasm requiring intensive treatment in an emergency room or at home, blood dyscrasias or convulsions that do not result in inpatient hospitalization, or the development of drug dependency or drug abuse (21 CFR 312.32).

- Important medical events as defined above, may also be considered serious adverse events. Any important medical event can and should be reported as an SAE if deemed appropriate by the Principal Investigator or the IND supporter, IND Office.
- All events occurring during the conduct of a protocol and meeting the definition of a SAE must be reported to the IRB in accordance with the timeframes and procedures outlined in "The University of Texas M. D. Anderson Cancer Center Institutional Review Board Policy for Investigators on Reporting Serious Unanticipated Adverse Events for Drugs and Devices". Unless stated otherwise in the protocol, all SAEs, expected or unexpected, must be reported to the IND Office, regardless of attribution (within 5 working days of knowledge of the event).
- All life-threatening or fatal events, that are unexpected, and related to the study drug, must have a written report submitted within 24 hours (next working day) of knowledge of the event to the Safety Project Manager in the IND Office.
- Unless otherwise noted, the electronic SAE application (eSAE) will be utilized for safety reporting to the IND Office and MDACC IRB.
- Serious adverse events will be captured from the time of the first protocol-specific intervention, until 30 days after the last dose of drug or earlier if the participant withdraws consent or starts a new anti-cancer therapy. Serious adverse events must be followed until clinical recovery is complete and laboratory tests have returned to baseline, progression of the event has stabilized, or there has been acceptable resolution of the event.
- Additionally, any serious adverse events that occur after the 30 day time period that are related to the study treatment must be reported to the IND Office. This may include the development of a secondary malignancy.

Reporting to FDA:

• Serious adverse events will be forwarded to FDA by the IND supporter (Safety Project Manager IND Office) according to 21 CFR 312.32.

It is the responsibility of the PI and the research team to ensure serious adverse events are reported according to the Code of Federal Regulations, Good Clinical Practices, the protocol guidelines, the supporter's guidelines, and Institutional Review Board policy.

5.4. Adverse Event Follow-Up

Patients are to be monitored for AEs throughout the treatment period and for a minimum of 30 days after their last dose of BXCL701. Longer AE follow-up is required, if necessary, to document recovery from AEs considered related to study medication. For patients who discontinue study medication due to an AE, repeated observations of that AE (or laboratory abnormality) must be made at intervals not exceeding 30 days until recovery is documented.

No further reporting of new AEs is required after the initiation of any subsequent chemotherapy or more than 30 days following the last dose of study medication, unless the study medication is considered to have contributed to the new AE.

5.5. Pharmacokinetic Assessments

Pharmacokinetic (PK) testing is not planned for this study since PK profiles of both agents are well known

5.6. Pharmacodynamic Assessments

Tumor biopsies (optional for Lead-in Stage and Stage 1 of Efficacy Stage [BOP1]; mandatory for Stage 2 of Efficacy Stage [BOP2]) will be collected at the time points described in Appendix A (Section 12) and the Laboratory Manual. Examples of biomarker analysis of tumor biopsies include immunohistochemistry, RNA sequencing or Nanostring. Whole blood samples (optional for Lead-in Stage and Stage 1 of Efficacy Stage [BOP1]; mandatory for Stage 2 of Efficacy Stage [BOP2]) will be collected at the time points described in Appendix A (Section 12) and Laboratory Manual. Examples of analysis include relevant immune effector cytokines, target engagement, testing of circulating tumor DNA (ctDNA).

5.7. Removal of Patients from the Study

Every effort within the bounds of safety and patient choice should be made to have each patient complete the treatment period of the study. Patients who have treatment discontinued due to PD may be treated with any additional therapy deemed appropriate by the investigator. Patients with disease progression per RECIST and/or iRECIST can continue on therapy for clinical benefit if deemed appropriate by the investigator.

Patients may be discontinued from the study for any of the following reasons:

- Investigator recommends discontinuation and documents the reason(s)
- There is a need for any treatment not allowed by the protocol
- Patient's decision to withdraw consent or discontinue for any reason
- There is an unacceptable AE thought to be related to study medication

Any patient who discontinues during the treatment period should return to complete safety and disease assessments (see Appendix A]).

5.8. Study Completion

The study will be considered complete when all patients have been followed to disease progression; are lost to follow-up, death, or withdrawal due to toxicity; patient's request; or investigator's discretion; and have completed all end-of-study treatment procedures.

6 STUDY MEDICATION

Study medication will be administered in 21-day cycles. Either BXCL701 or pembrolizumab may be administered first. However, on Cycle 1 Day 1, it is recommended that pembrolizumab be administered first and that \geq 1 hour should elapse before the administration of BXCL701 so that it will be easier to determine the relatedness of any AEs to study drug.

6.1 BXCL701 Dosage and Administration

BXCL701 tablets contain valine-proline boronic acid formulated as the methanesulfonate salt. Current dosage strengths include 0.1 mg and 0.05 mg tablets for oral administration.

BXCL701 will be administered orally as 0.1 mg and 0.05 mg tablets. BXCL should not be taken on an empty stomach. For a dose of 0.3 mg, patients will take 3 x 0.1 mg tablets and together. Patients will take 0.3 mg of the study drug twice a day, on days 1 to 14 of each cycle, for a total daily dose of 0.6 mg. BXCL701 will be continued until disease progression or unacceptable toxicity. Starting from Protocol version 7, newly enrolled patients will be administered BXCL701 at the starting dose of 0.2 mg (2 x 0.1 mg) orally twice a day. If well tolerated and in the absence of signs and symptoms of clinically significant hypotension the dose will be escalated to 0.3 mg (3 x 0.1 mg) orally twice a day.

To minimize risk of hypotension, patients should be advised to maintain adequate hydration while on-treatment, such as drinking at least 2 liters of fluids per day, including fluids with electrolytes. Factors such as strenuous exercise, heat, humidity, fever, gastrointestinal disturbance may increase hydration needs. Administration of at least 1L of IV fluids is recommended if not medically contraindicated at Cycle 1 Day 1. It is at the investigator's discretion to provide IV hydration during in-person clinic visits beyond Cycle 1 Day 1.

On days when pharmacodynamic studies are being performed, BXCL701 should be administered at the study center, and should be administered at (approximately) the same time of day on each treatment day in the cycle. In cycles in which pharmacodynamics are not evaluated, BXCL701 also should be administered at (approximately) the same time of day on each treatment day in the cycle, preferably 0800 hours. If the patient forgets to take study medication the dose will be skipped.

6.2 Dose Adjustments of BXCL701 Secondary to Toxicity

BXCL701 dose modifications (other than recommended in the protocol) within a treatment cycle are discouraged in Cycle 1 unless required by AE and/or DLT. In Cycle \geq 2, dose modifications within a treatment cycle will be at the discretion of the investigator. Doses held because of AEs should not be made up on subsequent days within or following a cycle. A dose that is missed for reasons other than an AE (i.e., the patient forgets to take a dose) may be administered on days subsequent to scheduled doses; any such adjustments should be discussed with the Investigator. Under no circumstances should missed doses be made-up on a day when the patient is already taking a planned dose (i.e., no "doubling-up" to account for missed doses).

Recommendations for BXCL701 dose modifications are:

- Do not administer BXC701 if systolic blood pressure obtained before dosing is less than 100 mmHg
- Grade 2 or higher AEs of edema/peripheral swelling, hypotension, dizziness, and hypovolemia:

- \circ For Grade 3 AEs, hold/interrupt BXCL701until resolution of these AEs to \leq Grade 1 or baseline. Thereafter, restart BXCL701 at a dose reduced by 0.2 mg (reduction of 0.1 mg twice day to 0.2 mg twice a day; 1 dose level reduction).
- For Grade 2 AEs, hold/interrupt BXCL701 until resolution of these AEs to \leq Grade 1 or baseline. Thereafter, resume at the full dose or at a dose reduced by 0.2 mg (reduction of 0.1 mg twice day to 0.2 mg twice a day; 1 dose level reduction) at the discretion of the investigator.
- For any Grade 3 or higher edema or Grade 2 edema that has not improved within 7 days, restart BXCL701 at a dose reduced by 0.2 mg (reduction of 0.1 mg twice day to 0.2 mg twice a day; 1 dose level reduction) after resolution of the edema to ≤ Grade 1 or baseline.
- For other Grade 2 or higher AEs deemed related to BXCL701:
 - Hold BXCL701 until resolution of these AEs to \leq Grade 1 or baseline.
 - For Grade 2 AEs, restart BXCL701 at the full dose or at a dose reduced by 0.2 mg (reduction of 0.1 mg twice day to 0.2 mg twice a day; 1 dose level reduction) at the discretion of the Investigator.
 - For Grade 3 AEs, restart BXCL701 at a dose reduced by 0.2 mg (reduction of 0.1 mg twice day to 0.2 mg twice a day; 1 dose level reduction).
- Once BXCL701 dose has been de-escalated, it may **not be** re-escalated.
- A maximum of 2 dose reductions per participant will be permitted for BXCL701-related AEs, after which the study drug will be permanently discontinued.
- Adverse events deemed related to BXCL701 not recovering to ≤ Grade 1 or baseline within 6 weeks from onset will require permanent discontinuation of BXCL701.
- Discontinue BXCL701 for any life-threatening AE.

If an SAE thought to be related to BXCL701 occurs during the Treatment Period, dosing of BXCL701 should be interrupted in that patient until the SAE resolves. If the Investigator wishes to continue the patient on BXCL701, the supporter should be contacted to discuss continuing BXCL701 at the same or reduced dose.

If BXCL701 is discontinued due to an AE, all termination from treatment procedures and assessments must be performed.

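### The five dose-reduction instructions in Section 6.2 print an end dose that is right only for a patient on 0.3 mg twice a day

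*Combined protocol and SAP*

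**What the plan says.** Section 6.1 sets the regular dose at 0.3 mg twice a day on Days 1 to 14 of each cycle. Under version 7 of the protocol and later ones, "newly enrolled patients will be administered BXCL701 at the starting dose of 0.2 mg (2 x 0.1 mg) orally twice a day"; Sections 3 and 3.1 give the length of that step as the first 7 days. The move up is conditional: "If well tolerated and in the absence of signs and symptoms of clinically significant hypotension the dose will be escalated to 0.3 mg".

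Section 6.2 then sets out what to do after toxicity, in a list introduced by "Recommendations for BXCL701 dose modifications are". Five entries contain a dose reduction. For Grade 3 edema, hypotension, dizziness or hypovolemia, BXCL701 is held until the event settles, and the physician is then to "restart BXCL701 at a dose reduced by 0.2 mg (reduction of 0.1 mg twice day to 0.2 mg twice a day". The bracket closes by calling this one dose level. The same bracket appears in the Grade 2 counterpart, where the physician may "resume at the full dose or at a dose reduced by 0.2 mg". It appears again in the separate edema rule, and in the Grade 2 and Grade 3 rules for other events related to BXCL701. None of the five names the dose the patient is coming from, and none presents the bracket as an example.

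The same section allows at most two reductions per participant and bars any later increase (the rule that begins "Once BXCL701 dose has been de-escalated").

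**The concern.** Each bracket states both how much to take off and where the patient ends up. A fixed cut paired with a fixed destination can be consistent from one starting dose only, and the protocol does not keep every patient at that dose. Two groups will be on 0.2 mg twice a day when an instruction is applied:

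- patients already reduced once from 0.3 mg twice a day who need the second reduction that Section 6.2 permits, whichever protocol version they enrolled under;
- version 7 patients in the step-up week, or not escalated because they did not meet the tolerance condition.

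For both groups the printed destination is the dose they were already taking. What is at stake is the restart dose after toxicity, including Grade 3 events. The step-up week matters here because Section 3.1 gives early hypotension as the reason for stepping up, and hypotension is one of the events these instructions govern. In Cycle 1, Section 6.2 discourages changes other than the recommended ones unless an AE or DLT requires them, so the printed recommendation is what a treating physician would consult.

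**Working it through.** Inputs:

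- Regular dose: 0.3 mg twice a day, 0.6 mg a day (Section 6.1).
- Step-up dose: 0.2 mg twice a day, 0.4 mg a day (Section 6.1).
- Cut: 0.2 mg a day, given in the bracket as 0.1 mg per dose (Section 6.2).
- Printed end dose: 0.2 mg twice a day, so 2 x 0.2 = 0.4 mg a day (Section 6.2).
- Reductions permitted: at most two (Section 6.2).

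Formula: dose per administration after one reduction = (2 x current dose - 0.2) / 2.

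| Patient's dose before the reduction | Dose from the cut | Printed end dose | Agree? |
|---|---|---|---|
| 0.3 mg twice a day | (0.6 - 0.2) / 2 = 0.2 mg twice a day | 0.2 mg twice a day | yes |
| 0.2 mg twice a day | (0.4 - 0.2) / 2 = 0.1 mg twice a day | 0.2 mg twice a day | no: printed dose is no reduction |
| 0.1 mg twice a day | (0.2 - 0.2) / 2 = 0, i.e. stop | 0.2 mg twice a day | no: printed dose is an increase |

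The first row reproduces the plan's own figure, so the bracket is arithmetically right from 0.3 mg twice a day. The second row is the contradiction: the cut gives 0.2 mg a day and the printed end dose gives 0.4 mg a day, a twofold difference within one sentence. The third row only shows where the ladder ends.

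Where the bracket occurs in Section 6.2:

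1. Grade 3 edema, hypotension, dizziness or hypovolemia: reduction, no full-dose option.
2. Grade 2 of the same events: full dose or reduction, at the investigator's discretion.
3. Edema of Grade 3 or higher, or Grade 2 not improved within 7 days: reduction, no full-dose option.
4. Grade 2 other related events: full dose or reduction, at the investigator's discretion.
5. Grade 3 other related events: reduction, no full-dose option.

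That is five of five with the fixed end dose, and three of five where a reduction is the only restart instruction. These are counts of one repeated phrase, not five separate errors, and entries 1 and 3 overlap for Grade 3 edema.

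Does any other text settle the restart dose? No dose-level table appears, and 0.1 mg twice a day is not named as a level in this trial. The lowest level named is the 0.4 mg daily lead-in fallback in Section 3.

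**The case against.** The strongest reply is that the operative rule is clear and only a leftover phrase is wrong. Each instruction expresses the step in three ways: a cut of 0.2 mg, a cut of 0.1 mg at each of the two doses, and one dose level. All three lead from 0.2 to 0.1 mg twice a day. The lower level can also be worked out: two reductions of this size from 0.3 mg twice a day can only end at 0.1 mg twice a day, and Section 6.1 confirms the tablets exist ("Current dosage strengths include 0.1 mg and 0.05 mg tablets for oral administration"). This reply largely stands on intent. It does not remove the conflicting dose, which is printed without any limit on whom it applies to.

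There are also safeguards. The list is framed as recommendations. From Cycle 2, "dose modifications within a treatment cycle will be at the discretion of the investigator". The trial is at one institution. BXCL701 is held until the event returns to Grade 1 or baseline, and is not given when systolic pressure is below 100 mmHg. The schedule in Appendix A has blood pressure checks before each dose and, in Cycle 1, frequent visits and safety calls. The supporter is contacted after a related SAE. These limit the risk, and an unreduced restart would probably be noticed quickly. None of them states the restart dose.

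A reader might infer more than the documents support:

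- That patients on 0.2 mg twice a day will be restarted unreduced. The sentence calls the step a reduction and gives its size, so a careful physician would probably choose 0.1 mg twice a day.
- That a version 7 patient reduced before escalation is denied a promised second reduction. Section 6.2 sets a maximum of two, and stopping after one does not breach it.
- That 0.1 mg twice a day is too low to be acceptable because Section 3.1 supports 0.4 to 0.6 mg daily. That range justifies the treatment dose; a reduction for toxicity need not stay within it. Section 3.1 also reports marked DPP-IV inhibition from 0.1 mg upward, and Section 1.3.2 describes patients treated at doses from 0.2 mg.

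**Conclusion.** The contradiction is real but limited. In all five reduction instructions, the cut and the end dose agree only for a patient on 0.3 mg twice a day. From 0.2 mg twice a day they give 0.1 mg twice a day and no reduction, respectively. Section 6.2 itself makes this foreseeable by permitting a second reduction, and the version 7 step-up adds a further group. The cut is the likely intent; the printed end dose is probably wording that fits only patients who were all on 0.3 mg twice a day, although the documents do not say so.

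The conclusion rests on the printed wording and simple subtraction. It assumes nothing about how often reductions occur, and the number of patients affected cannot be computed from the documents. It has no bearing on the sample size, the 9- and 17-patient decision rules or the error rates in Section 7, and should not be read as a concern about the response analysis. It should still be corrected, because a safety instruction ought to give one restart dose.

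**What to change.** Either delete the words *to 0.2 mg twice a day* from the five brackets, leaving the cut as the rule, or replace the brackets with a short dose-level table: 0.3, 0.2 and 0.1 mg twice a day, then discontinue. The table is the clearer choice because it states the level that a physician must now infer. In either case the sponsor should confirm 0.1 mg twice a day as the lowest level, since the protocol does not name it.

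The cost is five deletions or one small table in the next amendment. No patients, procedures or analyses are added.

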6.3 Monitoring of Patient Compliance with BXCL701 Study Medication

All BXCL701 dosing containers must be returned to the clinic at each visit. Patients should be queried regarding their compliance with the dosing regimen and medication containers should be reviewed at each visit to determine if any doses of BXCL701 have been missed, and the number of missed doses recorded. Patients must be at least 70% compliant with taking BXCL701 in Cycles 1 and 2 in order to be included in the per-protocol efficacy analyses.

6.4 BXCL701 Description and Storage

BXCL701 is supplied as 0.1 mg and 0.05 mg tablets in high-density polyethylene bottles with desiccant and child-resistant caps. 90 tablets will be provided in each bottle of 0.1 mg and 0.05 mg tablets. Supplies of BXCL701 will be appropriately labeled for clinical trial material. BXCL701 should be stored under refrigerated conditions between 2°C to 8°C (36°F to 46°F).

6.5 Pembrolizumab Administration, Dose Modifications and Discontinuation

Pembrolizumab will be prepared, stored, and administered according to the current full Prescribing Information. Pembrolizumab will be obtained from commercial supplies and will be administered 200 mg intravenously over 30 minutes through a 0.2 to 5 micron sterile, nonpyrogenic, low-protein binding online or add-on filter. No other medication will be infused through the infusion line. Infusion will be interrupted and slowed for grade 1 or 2 infusion-related reactions and permanently discontinued for grade 3 or 4 infusion-related reactions. Pembrolizumab will be administered until disease progression, unacceptable toxicity, or withdrawal of consent.

AEs associated with pembrolizumab exposure may be immune-mediated. Immune-related AEs may occur any time after pembrolizumab administration and may affect multiple body systems. Early recognition and treatment are important to reduce complications. Most immune-related AEs are reversible and can be managed with discontinuation of pembrolizumab and initiation of steroids. Refer to the current regional pembrolizumab full Prescribing Information for recommended dose modifications for the management of toxicities (including immune-mediated reactions and infusion-related reactions) considered related to pembrolizumab. Patients who require a dose hold of pembrolizumab of \geq 42 days will be discontinued from the study.

Pembrolizumab should not be used in conjunction with other immunosuppressive agents other than corticosteroids administered for control of immune reactions considered related to pembrolizumab. Refer to the current regional pembrolizumab full Prescribing Information for further details.

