5.3. Safety Assessments

5.3.1. Non-Serious Adverse Events

An Adverse Event is defined as any untoward medical occurrence in a patient regardless of its causal relationship to study treatment. An AE can be any unfavorable and unintended sign (including any clinically significant abnormal laboratory test result), symptom, or disease temporally associated with the use of the study treatment, whether or not it is considered to be study drug(s) related. Included in this definition are any newly occurring events and any previous condition that has increased in severity or frequency since the administration of study therapy. Investigators should assess for AEs at each visit. All AEs, including observed or volunteered problems, complaints, or symptoms, are to be recorded on the eCRF. Each AE is to be evaluated for duration, intensity, and causal relationship with the study treatment or other factors. MOCLIA will be used for eCRF in this study. Department (Investigational Cancer Therapeutics) database team will create the CRF based on protocol requirement and IND monitor will review and approve it once ready.

The investigator is responsible for monitoring the safety of patients who have entered the study. All AEs occurring during the treatment period and/or occurring within 30 days of the last dose of BXCL701 and or pembrolizumab (investigational products, IPs) will be followed to the end of the study or until resolution. AEs will be graded according to the revised NCI CTCAE, Version 5.0, (see http://ctep.cancer.gov/reporting/ctc.html). AEs occurring 30 days after the last dose of IPs do not need to be reported unless the investigator considers the event to be related to IPs.

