7.1 Safety Analyses

All patients in the safety population will be included in the final summaries and listings of safety data for the lead-in patients. Summaries of AEs and other safety parameters will be provided as appropriate. Emphasis in the analysis of AEs will be placed on those that are treatment-emergent through 30 days after last dose of BXCL701 with pembrolizumab

Frequencies of patients experiencing at least 1 AE will be displayed by body system and preferred term according to Medical Dictionary for Regulatory Activities (MedDRA) terminology. Detailed information collected for each AE will include: a description of the event, duration, whether the AE was serious, nature of the event (single episode versus multiple episode), intensity (i.e., NCI CTCAE version 5 grade), relationship to study drug, action taken, clinical outcome, and whether the AE resulted in surgery or alternate procedures. Intensity (severity) of the AEs will be graded according the NCI CTCAE. The latest version of MedDRA and NCI CTCAE will be used.

Summary tables will be prepared to show the number of patients reporting AEs, the frequency of patient reports, and corresponding percentages. Percentages will be calculated using the number of patients in the safety population as the denominator. Within each table, the AEs will be categorized by MedDRA body system and preferred term. Additional subcategories will be based on event intensity and relationship to study drug. AE data will be presented across all cycles and for each cycle. The denominator for each cycle is those patients available at the start of the cycle who received a dose of BXCL701 for that cycle.

To the extent possible, AE relationship to either BXCL701 or pembrolizumab will be identified.

Individual patient listings will be prepared for all AE data.

Vital signs and ECOG performance status will be summarized by visits/cycles, using descriptive statistics applicable to continuous or categorical measures of these additional safety data. Summaries for the Lead-in and Efficacy Stages will be presented.

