8.5.1 Discontinuation/Withdrawal Criteria

- A patient may be withdrawn by the investigator or the supporting company if he/she violates the study plan or for administrative and/or other safety reasons.
- The patient withdraws consent at any time after agent administration. Every effort will be made to determine why any subject withdraws from the study prematurely.

- The patient is lost to follow-up. A genuine effort must be made to determine the reason(s) why a patient fails to return for the necessary visits. If the subject is unreachable by telephone, a registered letter, at the minimum, should be sent requesting him/her to contact the clinic.
- Disease progression. RECIST 1.1 and iRECIST will be used for assessment of tumor response for the purposes of managing patients on protocol treatment and decision making for discontinuation of study therapy due to disease progression. Response assessments with CT and/or MRI will be done every 9 weeks (3 cycles) following RECIST and iRECIST criteria (intervals can be shortened to 6 weeks if clinically necessary per treating physician). Patients with disease progression per RECIST and/or iRECIST can continue on therapy for clinical benefit if deemed appropriate by the investigator.
- The patient starts a new anti-cancer therapy
- There is a need for any treatment not allowed by the protocol
- Any life-threatening AE.

Any adverse experiences that are present at the time of discontinuation/withdrawal should be followed in accordance with the safety requirements outlined in Section 5.3 Safety Assessments.

Patients who discontinue study treatment who have not shown disease progression and have not withdrawn consent will continue to be followed for disease progression and survival.

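### Per-cycle adverse event rates in Section 7.1 count only patients dosed with BXCL701, although pembrolizumab can continue without it; related stopping rules and follow-up windows need aligning

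*Combined protocol and SAP*

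**What the plan says.** **Per-cycle denominator.** Section 7.1 presents AEs across all cycles and by cycle. For the by-cycle tables it states: "The denominator for each cycle is those patients available at the start of the cycle who received a dose of BXCL701 for that cycle". It does not say whose events form the numerator.

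**Stopping each drug.** Section 6.1: "BXCL701 will be continued until disease progression or unacceptable toxicity". Section 6.5, for the other drug: "Pembrolizumab will be administered until disease progression, unacceptable toxicity, or withdrawal of consent". Section 6.2 holds BXCL701 for related AEs of Grade 2 or higher. It requires permanent discontinuation after two dose reductions, or when a related AE has not recovered within 6 weeks of onset.

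**Consequences of stopping.** Section 6.2 says "Discontinue BXCL701 for any life-threatening AE" and "If BXCL701 is discontinued due to an AE, all termination from treatment procedures and assessments must be performed". Section 8.5.1 lists "Any life-threatening AE" among the criteria for withdrawing the patient.

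**AE windows.** The first sentence of 5.4 monitors patients during the treatment period and "for a minimum of 30 days after their last dose of BXCL701". Section 5.3.1 covers AEs during treatment or "occurring within 30 days of the last dose of BXCL701 and or pembrolizumab". The second paragraph of 5.4 ends reporting of new AEs 30 days after study medication, not BXCL701 specifically. The treatment-emergent window in 7.1 names the two drugs together, and can be read as the last dose of the pair or the last dose of either.

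**The concern.** The study tests a combination, but its per-cycle safety tables are defined by exposure to one component. A patient whose BXCL701 is held through a cycle, and who still receives pembrolizumab on Day 1, is exposed to a study drug, can have an AE, and is not in the denominator. The omission is informative, because BXCL701 is typically held for toxicity: the patients removed from a cycle's rate are those who tolerated treatment poorly in the cycle before. Section 6.5 itself warns that immune-related AEs may occur at any time after pembrolizumab.

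The other passages matter because they determine how many such patients there are and how long they are followed. A site has no single statement of whether pembrolizumab goes on once BXCL701 is permanently stopped, and the AE sections give different reference dates for the 30-day period.

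**Working it through.** The plan gives no figure for per-cycle AE rates, so there is none to reproduce. The check is whether the situation can arise, and what the stated denominator then does.

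**1. Can a cycle contain pembrolizumab but no BXCL701?** Cycles last 21 days, with BXCL701 on Days 1 to 14 and pembrolizumab on Day 1. The recovery limit in 6.2 is 6 weeks = 42 days = 42/21 = 2 cycle lengths. Take a related AE starting on study Day 10:

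- Recovery may take until Day 10 + 42 = Day 52.
- BXCL701 dosing in Cycle 2 falls on Days 22 to 35, entirely inside the hold.
- Pembrolizumab is due on Day 22, and nothing in 6.5 stops it for a BXCL701 hold.

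So a Cycle 2 without BXCL701 is possible without permanent discontinuation. This assumes the site does not delay the whole cycle. A patient who takes even one BXCL701 dose in a cycle stays in the denominator, so only holds spanning a cycle's dosing days matter.

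**2. Effect on the rate.** Let N be the patients receiving either drug in a cycle, m those with no BXCL701 in it, and a and b the patients with the AE among the N − m dosed and the m undosed.

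- Either-drug rate: (a + b)/N.
- Reading 1, all events over the 7.1 denominator: (a + b)/(N − m). This is too high by the factor N/(N − m) whenever there is any event.
- Reading 2, only BXCL701-dosed patients' events: a/(N − m). This is below the either-drug rate if b/m exceeds a/(N − m), above it if b/m is smaller, and equal if they match.

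The counts below are assumed; the documents give no number of patients on pembrolizumab alone.

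| N | m | a | b | Either drug | Reading 1 | Reading 2 |
|---|---|---|---|---|---|---|
| 10 | 3 | 1 | 1 | 2/10 = 20% | 2/7 = 29% | 1/7 = 14% |
| 12 | 2 | 3 | 1 | 4/12 = 33% | 4/10 = 40% | 3/10 = 30% |
| 12 | 4 | 2 | 2 | 4/12 = 33% | 4/8 = 50% | 2/8 = 25% |
| 12 | 4 | 2 | 1 | 3/12 = 25% | 3/8 = 38% | 2/8 = 25% |

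The direction depends on a numerator rule that 7.1 does not give.

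**3. Stopping rules side by side.**

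- Life-threatening AE: 6.2 acts on BXCL701; 8.5.1 acts on the patient.
- BXCL701 stopped for an AE: 6.2 calls for termination procedures, while 6.5 does not list this among the reasons to end pembrolizumab. Appendix A ties the end-of-treatment visit to stopping the study drugs, in the plural.
- Long holds: 6.5 takes a patient off study after a pembrolizumab hold of 42 days or more; there is no counterpart for a BXCL701 hold.

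No sentence expressly permits or expressly ends pembrolizumab alone.

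**4. Reference date for the 30 days.** It is BXCL701 in the first sentence of 5.4; either drug in 5.3.1; study medication in the 5.4 reporting cut-off; the last dose of drug for serious AEs in 5.3.2; and ambiguous in 7.1.

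**The case against.** The strongest defence is that little is lost. Overall AE percentages use the safety population, Section 3 includes in the safety analysis everyone with at least one dose of study drug, and 7.1 lists every AE individually. That stands, and confines the problem to the per-cycle tables. A BXCL701-dosed denominator also answers a fair question, the AE rate in cycles where both drugs were given, provided the numerator is matched. It should not be the only per-cycle rate.

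On stopping, the termination procedures in 6.2 are assessments and do not themselves stop pembrolizumab, and a drug-level rule in 6.2 can be followed together with a patient-level criterion in 8.5.1. This is fair: it is an implied conflict plus silence, not an express contradiction. A site still has to guess.

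A reader might infer that AEs on pembrolizumab alone go uncollected. The documents do not support that. The 5.4 sentence sets a minimum and also covers the treatment period; Section 6 treats both drugs as study medication; 5.3.1, 5.3.2 and the 5.4 reporting cut-off are not limited to BXCL701; and Appendix A schedules AE assessment on Day 1 of every cycle, at end of treatment and at follow-up. The fault is inconsistent wording.

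A reader might also infer that responses on pembrolizumab alone are credited to the combination and inflate the chance of a promising result. Section 7 is silent on responses after BXCL701 stops. Counting them would be a legitimate treatment-policy choice, and a single arm cannot isolate BXCL701's contribution either way. Section 6.3 also sets a 70% BXCL701 compliance condition in Cycles 1 and 2 for per-protocol efficacy analyses, though Section 7 does not link it to the decision rule. Inflation above the null calculation would require assuming that pembrolizumab alone outperforms the combination, for which the documents give no basis.

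**Conclusion.** The point holds for the per-cycle AE tables. As written, 7.1 leaves pembrolizumab-treated patients out of a cycle's rate when they took no BXCL701 in it, and the undefined numerator allows error in either direction. In the examples, reading 1 overstates the either-drug rate by a factor of 1.2 (12/10) to 1.5 (12/8), and reading 2 ranges from no difference to about 8 percentage points too low (25% against 33%). These sizes rest on assumed counts and on pembrolizumab being given on schedule during a BXCL701 hold.

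The inconsistencies among 6.2, 6.5 and 8.5.1, and between the first sentence of 5.4 and 5.3.1, are real and need reconciling. Nothing here shows overall AE percentages, sample size or the stated operating characteristics to be wrong. The change should be made, but it does not threaten the primary analysis.

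**What to change.** - **Section 7.1, per-cycle tables:** use as denominator the patients who received either study drug in the cycle, and draw the numerator from the same patients. A BXCL701-dosed subset, with its own matched numerator, may be shown beside it.
- **Sections 5.4 and 7.1, window:** run the 30 days from the last dose of either drug, meaning the later of the two last doses, as 5.3.1 does.
- **Sections 6.2, 6.5 and 8.5.1:** reconcile them so that they give one instruction on pembrolizumab when BXCL701 is permanently stopped, including after a life-threatening AE. Which rule is clinically right is for the investigator and sponsor to decide; this review takes no view.

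The cost is amendment wording, a small change to the table programs, and slightly more AE follow-up in patients who stay on pembrolizumab.
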